## 12.0 Provisions to Monitor the Data to Ensure the Safety of Subjects

**12.1 DoD Independent Research Monitor.** The Research Monitor, the PERCePT Data and Safety Monitoring Board, is responsible to oversee the safety of the research and report observations and findings to the IRB. The Research Monitor will review all unanticipated problems involving risks to subjects or others associated with the protocol and provide an independent report of the event to the IRB. The Research Monitor may discuss the research protocol with the investigators; shall have authority to stop a research protocol in progress, remove individual human subjects from a research protocol, and take whatever steps are necessary to protect the safety and well-being of human subjects until the IRB can assess the monitor's report; and shall have the responsibility to promptly report their observations and findings to the IRB and the HRPO.

## 13.0 Withdrawal of Subjects

- The participant has the right to voluntarily withdraw consent from the study at any time for any reason without prejudice to his/her future medical care by the physician or at the institution. For the occasional participant who withdraws consent, the date and reason for consent withdrawal should be documented. Participant data will be included in the analysis up to the date of the consent withdrawal.
- A distinction should be made between participants who fail to complete all forms on schedule, who miss some telephone visits, and the withdrawal of consent. Missed or rescheduled visits will be documented, but the participant will continue to be followed in the future according to protocol requirements, and all follow-up data will be included in the analysis.
- If the participant withdraws consent for the protocol intervention and/or study related procedures, document whether the participant is willing to allow the submission of continued follow-up information. This documentation should include whether the subject will continue to be willing to be contacted during

follow-up to complete all questionnaires, or at a minimum will be willing to be contacted to provide information on quality of life.

- Investigators and/or the sponsor may stop a subject's participation in the study at any time if they decide it is in the subject's best interest. They may also do this if the subject does not follow the investigator's instructions.

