## **4.0 Study Endpoints**

### **4.1 Pilot primary outcome**

The primary efficacy outcome for this pilot study will be average daily pain from the electronic diaries during the 14-day period preceding the 90-day assessment, compared to the average daily pain reported during the 14-day run-in. Clinical improvement will be defined by the change in the average pain score between these two intervals, and without the need for increased opioids or additional interventions/procedures. A standardized 11-point Numeric Rating Scale (NRS) will be used to capture average daily pain with the empirically-supported anchors of 0=No Pain and 10=Worst Pain Imaginable.

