**Table 1. Summary of Study procedures\***

Visit	Details
Screening visit	
 
Patient seen in pancreatobiliary clinic for painful chronic pancreatitis
 
Review eligibility criteria
 

Informed consent	
 
Obtain informed consent
 

Run-in period (approximately - 14 to 0 days)	
 
Subject provides daily diary for approximately 14 days (Ecological Momentary Assessment)
 

Quantitative Sensory Testing	
 
Complete Quantitative Sensory Testing prior to randomization procedure
 

Randomization visit (day 0)	
 
Confirm eligibility criteria
 
Finalize completion of baseline assessment instruments
 
Randomization procedures
 

Randomization procedures (day 0)	
 
Complete EUS + sham or EUS + ERCP with pancreatic endotherapy
 
No randomization procedure if observational subject.
 

Telephone contact (day 7)	
 
Telephone contact to confirm no procedure-related adverse events
 

Telephone contact (day 30)	
 
Telephone contact to confirm no procedure-related adverse events
 

Complete Daily Diary (days 0-30 and 76-90)	
 
Subject will complete daily diary for 30 days after randomization procedures (Ecological Momentary Assessment)
 
Subject will complete daily diary for the 14-day period leading up to their follow-up visit (days 76-90), which will be scheduled on day 90
 

Follow-up visit (day 90)	
 
Subject returns for in- person follow-up assessment (repeat baseline assessment instruments and quantitative sensory testing).           
 
Observational subject may complete visit by telephone
 
 
 
Repeat ERCP with pancreatic endotherapy if applicable (if stents are in place and require removal or upsizing)
 
Perform ERCP if failure to improve, subject is unmasked and found to be in sham group, and subject wishes to proceed with pancreatic endotherapy
 
Complete primary outcome measures
 

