**Table 3. Follow-up assessments in the PERCePT trial**

Outcome measures	Instrument(s)	Follow-up visit				Explanation and estimated completion time
		90	180	270	360	
Clinical evaluation	Blinded physician evaluation	X				
 
Assessment by a blinded gastroenterologist and pancreatobiliary surgeon
 

Patient characteristics	PERCePT study follow-up case report forms	X	X	X	X	
 
Data will be collected as applicable and available: history of acute pancreatitis episodes, opioid utilization, interventions performed and hospital encounters during the interval follow-up period
 
5-minutes
 

Harmful alcohol drinking	Alcohol Use Disorders Test	X	X	X	X	
 
Screening instrument for hazardous and harmful alcohol drinking
 

	(AUDIT) 					
 
• 2-minutes
 

Current pain disability	RAPID 	X			X	
 
• Pain-related disability (90-day recall); developed, validated, and used for the EPISOD study
 
• 3-minutes
 

Average daily pain, mood, activity-level, sleep and analgesic medication use	Ecological Momentary Assessment (EMA)	X				
 
• Electronic daily diaries designed to capture repeated measures of pain, activity, sleep, and opioid use
 
• Daily from days 0-30 and 76-90
 

Pain Severity and Functional Impairment	Brief Pain Inventory (BPI)	X	X	X	X	
 
• Measures pain at its worst, least, average, and at time of evaluation
 
• Measures patient perception of effectiveness of current pain medications
 
• Measures functional impairment due to pain
 
• 7-minutes
 

Quality of life	PROMIS 29 Profile	X	X	X	X	
 
• Assessment of anxiety, depression, fatigue, pain interference, physical function, sleep disturbance, ability to participate in social roles and activities, and a single pain intensity item
 
• 5-minutes
 

Laboratory Pain and Central Sensitization	Quantitative Sensory Testing (QST)	X				
 
• Thermal and mechanical pain threshold, pain tolerance, as well as wind-up and conditioned modulation testing to assess central pain facilitation and inhibition
 
• 1-hour follow-up visit
 

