**11.4 Statistical Analysis.** The analysis will be conducted according to the intention-to-treat (ITT) principle wherein subjects will be analyzed according to the assigned treatment. Several exploratory analyses and descriptive statistics will be examined, including covariates. Secondary analyses of additional outcomes, including change in QOL scores, disability, and depression, will be approached in a similar manner and considered exploratory using confident intervals rather than p values.

**11.5 Data Security and Confidentiality.** During the course of the trial, user access to the files with subject identifiers, and the files with study outcomes will be restricted to core staff with any exceptions to be approved by the Executive Committee. In addition to use of passwords and other security measures, all documents containing identifying information on individuals or physicians are considered confidential materials and will be safeguarded to the greatest possible extent. No information, which identifies a specific person, hospital, or physician, will be released to, or discussed with anyone other than study staff members.

**11.6 Quality Control.** Upon entry of CRFs into the study database, quality control procedures will be applied at each stage of data handling in order to ensure compliance with GCP guidelines, integrity of the study data, and document processing system reliability. The site will be monitored by the DCU and the site monitor will conduct periodic site visits to review source documents and case report form information. A quality assurance record audit will be implemented. Audit findings will be used to identify and correct problems.

**11.7 Web Based System.** Because the DCU uses a web-based system, source documents and CRFs will remain at the study site. This study database only identifies study subjects by unique study identification codes. All data will be stored in a manner that is HIPAA compliant, without the ability to track the information back to a specific subject except through a password protected system. All collected information about a subject will be stored by a unique identification code. All DCU personnel have completed human subject protection training and good clinical practice training.

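### No rule says how a randomized subject without a day 76-90 diary enters the ITT primary analysis, and no use of the day 0-30 diary is specified

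*Combined protocol and SAP*

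**What the plan says.** Section 4.1 defines the primary outcome as "average daily pain from the electronic diaries during the 14-day period preceding the 90-day assessment", compared with the run-in average. Table 3 gives the diary schedule after randomization as "Daily from days 0-30 and 76-90", so none is scheduled for days 31 to 75. Table 1 confirms the early block: "Subject will complete daily diary for 30 days after randomization procedures".

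On subjects who leave, Section 13.0 has three rules. For withdrawal of consent, "Participant data will be included in the analysis up to the date of the consent withdrawal". For subjects who only miss forms or visits, follow-up continues and "all follow-up data will be included in the analysis". For those who withdraw from the intervention or procedures, staff are to "document whether the participant is willing to allow the submission of continued follow-up information".

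Section 10.1.3 has the one substitution rule. If a subject is referred for re-intervention before day 90, the diary is reactivated for up to 14 days beforehand and those scores are used in the primary change score.

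Section 11.4 states: "The analysis will be conducted according to the intention-to-treat (ITT) principle wherein subjects will be analyzed according to the assigned treatment". It adds unspecified exploratory and descriptive analyses. It names no primary model, no missing-data method, no minimum number of diary days and no use of the day 0-30 diary.

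**The concern.** A subject who withdraws consent or is lost on, say, day 40 may have given a full run-in diary and a full early diary, yet has no value of the primary score as defined. The withdrawal rule says those data count and the ITT statement says the subject counts, but nothing says how. The sponsor foresaw a missing score for re-intervention and left the other routes open: consent withdrawal, loss to follow-up, diary non-response in the final window, and participation stopped by the investigator.

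With 15 per arm, each loss is 1/15, about 7% of an arm. Retention is one of the things the pilot is testing (Section 1.1), so complete follow-up cannot be taken for granted. Section 15.2 says the results are to feed the planning of a definitive trial. The effect and variance estimates therefore need a fixed, reproducible definition of who is in them.

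**Working it through.** **Who has a primary score under the stated rules**

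| Subject | Route to a primary score |
|---|---|
| Completes the day 76-90 diary | Section 4.1 |
| Re-intervened before day 90 | Section 10.1.3 substitute |
| Misses early diaries or visits, still followed | Section 4.1, since the diary restarts at day 76 |
| Leaves the procedures, agrees to follow-up | Possible, if the late diary is given |
| Withdraws consent or is lost before day 76 | None stated |

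The last row is the gap.

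**The plan's own figures.** There is no power, SD or dropout figure to reproduce. Section 11.2 gives 2 × 15 = 30, which agrees with 10 + 20 by site in Section 6.0.

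**Assumed inputs for size (none is in the documents).** SD 2.5 for each period mean. Correlations: run-in with early 0.6, run-in with late 0.5, early with late 0.7. True late difference -1.5. Loss of 20% in sham, rising with early pain, and 7% in ERCP, so about 12 and 14 analysed.

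**Standard errors by formula**
- SD of change = 2.5 × √(2 × (1 − 0.5)) = 2.50.
- Residual SD after baseline adjustment = 2.5 × √(1 − 0.5²) = 2.17.
- √(1/12 + 1/14) = 0.393.
- Change score SE = 2.50 × 0.393 = 0.98.
- Baseline-adjusted completers SE = 2.17 × 0.393 = 0.85.

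Baseline adjustment alone therefore gives 1 − 0.85/0.98, about 13%, before the early diary is used.

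**Why the two completers-only analyses differ in bias.** If sham loss depends on early pain, the bias scales with the correlation of early pain with whatever is analysed. For the change score this is 0.7 − 0.6 = 0.1. For the late score adjusted for run-in it is about 0.7 − 0.5 × 0.6 = 0.4, four times as large. The small bias of the change score thus reflects two assumed correlations that nearly cancel.

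**Simulation.** About 6,000 trials per scenario, logistic loss with slopes of 1 and 2 per SD of early pain, and early effects of -1.0 and -1.5. The likelihood estimate is the arm effect on the late mean given early and run-in means, plus the slope on the early mean times the run-in-adjusted arm effect on the early mean in all subjects.

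| Loss, sham / ERCP | Analysis | Bias toward null | SE |
|---|---|---|---|
| 20% / 7% | Change score, completers | about 0.06 | about 0.98 |
| | Baseline-adjusted, completers | 0.2 to 0.3 | about 0.87 |
| | Likelihood with early diary | about 0 | about 0.86 |
| 33% / 7% | Change score, completers | about 0.1 | about 1.05 |
| | Baseline-adjusted, completers | 0.3 to 0.4 | about 0.91 |
| | Likelihood with early diary | about 0 | about 0.90 |

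From change score to likelihood model the SE falls by (0.98 − 0.86)/0.98, about 12%. Like for like with the baseline-adjusted completers analysis, the early diary changes the SE by only about 0.01. With 20% loss alike in both arms there is no material bias, and the early diary again adds little (SE about 0.90 against 0.89).

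**The case against.** Much can be said for leaving the plan as it is. It is a feasibility pilot with no power claim. Section 13.0 expects only an occasional withdrawal, and no dropout rate is given. Subjects re-intervened before day 90 are covered. Sham subjects who fare badly can have open-label ERCP at day 90, which is a reason to stay. Stopping the early diary does not lose the late one. All of this stands, and it limits how many subjects the gap will touch.

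Three stronger readings are tempting, and the documents support none of them.

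- A reader might infer that early leavers are dropped. No text prescribes a completers-only analysis; that is inferred from silence.
- A reader might infer that the day 0-30 diaries enter no analysis. Section 11.4 allows unspecified exploratory and descriptive work that could use them. What is true is that no such use is specified.
- A reader might infer that ITT is contradicted and the primary result seriously biased. Section 11.4 explains ITT only as "subjects will be analyzed according to the assigned treatment", so this is an omission rather than a contradiction. Under the inputs above, the change score that the plan describes has negligible bias next to its SE. The larger bias belongs to a completers-only baseline-adjusted analysis that the plan never names.

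What remains is that a subject lost before day 76 has no defined place in the primary analysis, and that data able to give one are already being collected.

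**Conclusion.** The concern holds as a gap in specification. Apart from re-intervened subjects, nothing says how a randomized subject without a day 76-90 diary enters the ITT primary analysis, and the Section 13.0 inclusion rule cannot be carried out for that outcome as written.

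In numbers the case for change is moderate. A three-period likelihood model lowers the SE by about 12%, nearly all of it through baseline adjustment, and keeps every randomized subject who has a diary. The early diary earns its place by protecting the adjusted analysis from bias of 0.2 to 0.3 points, or up to about 0.4 with 33% sham loss. These sizes rest on assumed SD, correlations and loss rates, and on loss that depends on early pain in one arm. If loss is alike in both arms, the early diary gains little. The change should be made because it is cheap and settles the analysis before data are seen.

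**What to change.** In Section 11.4, replace the simple change score as the primary estimate with a baseline-adjusted, likelihood-based longitudinal model:

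- Three diary means per subject: run-in, a single day 1-30 mean, and day 76-90.
- Arm-by-period terms with a common baseline mean across arms.
- All randomized subjects with any diary included, by assigned arm.
- The arm contrast at day 76-90 as the primary estimate.
- The pre-intervention diary of Section 10.1.3 kept as the late value for re-intervened subjects.
- The change score kept as a sensitivity analysis.

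Use one early mean rather than weekly means. Three periods need 3 × 4/2 = 6 covariance parameters. Run-in, four weeks and the late window would need 6 × 7/2 = 21, too many for 30 subjects. Section 13.0 should then refer to this model as the way data before withdrawal are used.

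The cost is slightly more analysis work and no new data. The model relies on loss being missing at random given the run-in and early diaries. A simple check is to shift the leavers' late values: with 3 of 15 lost in one arm, a shift of 1, 2 or 3 points moves that arm's mean by 3/15 of the shift, that is 0.20, 0.40 or 0.60.

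### The minimum follow-up after withdrawal from procedures is quality of life, and neither tier of the rule names the diary pain that forms the primary outcome

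*Combined protocol and SAP*

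**What the plan says.** The third bullet of Section 13 is triggered by partial withdrawal: "If the participant withdraws consent for the protocol intervention and/or study related procedures, document whether the participant is willing to allow the submission" of further follow-up information. What the site must record then has two levels. The fuller level is willingness to be contacted during "follow-up to complete all questionnaires"; the lower is "or at a minimum will be willing to be contacted to provide information on quality of life". The first bullet covers full withdrawal of consent: "Participant data will be included in the analysis up to the date of the consent withdrawal".

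Section 4.1 sets the primary outcome: "The primary efficacy outcome for this pilot study will be average daily pain from the electronic diaries", taken over the 14 days before the day 90 assessment and compared with the 14-day run-in. Clinical improvement must also occur "without the need for increased opioids or additional interventions/procedures". Section 4.2 places quality of life among the secondary outcomes.

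Section 11.4 gives the analysis principle: "The analysis will be conducted according to the intention-to-treat (ITT) principle". It states no method for a missing day 76-90 diary.

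**The concern.** A withdrawal rule should hold on to the primary outcome first. Here the stated floor protects a secondary endpoint, and the primary is not mentioned at either level. The diary would suit a subject who refuses procedures: Section 10.1.1 has it delivered remotely, by telephone, text message or web link, and it already records opioid use, which Section 4.1 also needs.

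At stake is an avoidable gap in the primary data for a person the site can still reach. With 15 per arm, each such subject is a visible share of the comparison. Retention is itself a feasibility aim (Section 1.1), so the pilot's handling of these subjects also informs the definitive trial.

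**Working it through.** The plan states no figure on this point, so there is nothing to reproduce. The check is mainly a comparison of sections, with a short calculation for scale.

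**Does either tier secure the primary?**

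1. The outcome needed is "average daily pain from the electronic diaries during the 14-day period preceding the 90-day assessment" (Section 4.1). Tables 1 and 3 place the post-randomization diary on days 0-30 and 76-90 only.
2. The lower tier asks for quality of life. The instrument is PROMIS 29 (Tables 2 and 3), which contains one pain-intensity item. That is some pain information, with a baseline value, but it is a single answer and not a 14-day mean.
3. The upper tier asks for all questionnaires. The diary is listed as an instrument beside the questionnaires in Tables 2 and 3, so it can be read as included, but Section 13 does not say so.

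**Does another rule fill the gap?**

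4. Data before full consent withdrawal are kept (Section 13). A subject who leaves before day 76 has no data in the primary window; one who leaves between days 76 and 90 has part of it.
5. Section 10.1.3 reactivates the diary when a subject is referred for re-intervention before day 90, and uses those scores in the primary analysis. It does not extend this to withdrawal.
6. Section 11.4 has no missing-data method.

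The gap therefore needs all of the following: withdrawal from procedures before the day 76-90 diary is complete; continued contact; and either acceptance of the minimum only, or a site that does not treat the diary as a questionnaire. Withdrawal after day 90 does not touch the primary.

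**Scale**

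Inputs: 30 randomized, 15 per arm (Section 11.2). Assumed: 1 to 3 subjects lost per arm, equal in both arms, with unchanged SD. The documents give no withdrawal rate.

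- Share per subject: 1/15 = 6.7% of an arm; 1/30 = 3.3% of all randomized.
- The standard error of a difference in means is SD × √(2/n), so the ratio to the full sample is √(15/n):
  - n = 14: √(15/14) = 1.035, an increase of 3.5%
  - n = 13: √(15/13) = 1.074, an increase of 7.4%
  - n = 12: √(15/12) = 1.118, an increase of 11.8%

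In pain points, the 95% confidence half-width is t(0.975, 2n−2) × SD × √(2/n). The documents give no SD for the diary change score. The only pain SD is 2.8, for the BPI average-pain item in a cross-sectional study (Section 2.5), used here as an assumption with a range of 2.0 to 3.5.

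| Per arm | SD 2.0 | SD 2.8 | SD 3.5 |
|---|---|---|---|
| 15 | 1.50 | 2.09 | 2.62 |
| 14 | 1.55 | 2.18 | 2.72 |
| 13 | 1.62 | 2.27 | 2.83 |
| 12 | 1.69 | 2.37 | 2.96 |

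At SD 2.8, a loss of 3 per arm widens the half-width by 2.37 − 2.09 = 0.28 points.

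**The case against.** The strongest reply is that the rule governs what a site documents, not what it may collect. Nothing in it tells a site to stop the diary, and a site that keeps sending it to a willing subject complies fully. Reading the diary into the upper tier is natural. The randomized treatment is given once, immediately after allocation, and Section 13 itself describes consent withdrawal as occasional, so few subjects should fall into the gap. Quality of life is also a candidate outcome for the definitive trial (Section 1.2), which makes it a defensible floor. Asking a reluctant subject for daily messages could lose both endpoints.

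Most of this stands, and it rules out three stronger inferences that a reader might draw:

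- **That the rule as a whole loses the primary, or that a site following it exactly ends with no primary value.** The upper tier and the freedom to continue the diary contradict this.
- **That the primary comparison will be biased.** Withdrawal after an unhelpful sham or a painful ERCP could depend on outcome and differ by arm, but the documents give no rate or pattern, and the standard-error figures measure precision only.
- **That the rule breaks intention-to-treat.** Section 11.4 defines that principle as analysis by assigned arm, which this rule leaves unchanged. The missing-data method is a separate omission.

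What the reply does not remove is the ordering. Where a floor is stated, it names a secondary endpoint, and inclusion of the diary is left to each site's reading. The concern about burden is met by keeping quality of life as the last step.

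**Conclusion.** The point holds in a limited form. Section 13 names quality of life as the minimum follow-up after withdrawal from procedures and does not name diary pain at either level; no other section covers a withdrawn subject's day 76-90 window. The consequence is confined to reachable subjects who withdraw before that diary is complete and who either accept only the minimum or attend a site that does not count the diary as a questionnaire. Their number is unknown and probably small. The 3.5% to 11.8% rise in standard error rests on an assumed loss of 1 to 3 per arm. This is an inexpensive improvement to make in a 30-subject pilot, not a threat to the validity of the design.

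**What to change.** In the third bullet of Section 13 and the matching form, state that the electronic diary is one of the questionnaires, and replace the single minimum with an ordered request:

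1. The daily average-pain and opioid-use diary items for days 76-90, by text message, telephone or link, with any interventions recorded.
2. If declined, one contact at day 90 for the BPI average-pain item and quality of life. The BPI item has its own baseline (Table 2) and day 90 value (Table 3). It should be used only as supportive data against that baseline, because a single answer does not replace the 14-day mean.
3. If that is also declined, quality of life alone, as now.

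The cost is one revised bullet and its form, using the existing diary system. A willing subject receives up to about 14 short messages. Because quality of life remains the floor, it need not be lost when the diary is refused. The sample size does not change.
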